CTCAE version 4.0 will be used for registration of AE. In case of AE of grade 3 or 4 according to CTCAE occur for more than three days, the responsible investigator will act. The intake of cheese will be stopped and the XCS will be followed up until the symptoms disappear. The total duration from the last intake of the cheese to the disappearance of the symptoms will be recorded in days together with the treatment procedure. They will be reminded to fill in their dietary record.

6.2.4 Dietary monitoring:

The participants will fill in their dietary intake in an application at baseline and every 8th week of the study. During the last visit an Eating Disorder Examination Questionnaire- Short, derived from EDE-Q © Fairburn and Beglin⁴⁰, will be a part of the interview. The questions will be woven into the anamnestic interview and not as a questionnaire to ensure that the participants do not suffer from disordered eating.

6.3: Treatment administration of the study

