6.3.1 Administration and doses

At baseline (week 0) the female and male strata will be provided a cheese sample for 4 weeks consumption of the type of cheese group they are allocated into. The female participants will be provided a sample resembling 75 grams cheese (5 slices) a day, and the male participants

will be provided 90 grams (6 slices) per day. The dose of Jarlsberg and Norvegia cheese is equal, and the dose is fixed due to OED from the former dose-finding study. After 4 weeks all participants will be provided new cheese samples of their study cheese. This will be repeated every 4 weeks till the end of the study at 24 as described previously. The dose of Jarlsberg and Norvegia cheese is equal.

Energy Sources	Jarlsberg Cheese	Norvegia Cheese
Total Energy	1458 kJ (351 kcal)	1458 kJ(351kcal)
fat	27g	27 g
carbohydrates	0 g	0 g
protein	27g	27g
calcium	770mg	820mg
phosphate	550mg	590mg

Tabell II: Cheese Energy Contents per 100 grams

6.3.2 Cheese supply, packing and storage.

The cheese will be delivered in 250-gram packages. The participants will receive the cheese by the investigator every 4 weeks. Both the Jarlsberg- and the Norvegia cheese used in the study will be given free of charge to the participating athletes.

Each package is labelled in accordance with the procedure for clinical trials. Additionally, the participants will be informed on how to perform the intake of the cheese and to store the cheese in a refrigerator at a temperature from 4° to10°C. Expiry date will be printed on the label.

Description	For use only in clinical trial
Trial substance	Type of cheese
Expire date	
Administration	Oral intake
Investigator	
Name of exporter	TINE A/S:
[contact]
Study	Comparative study in Active XCS
EudraCT number	2022-003264-24
Protocol id	XCS-Jarlsberg/IIA
Storage	Refrigerator between 4° to10°C

Table III: Label on each package

6.4: Stopping rule

In case of life-threatening AE or Serious Adverse Events (SAE) occurs, the cheese intake must stop, and the participant treated and followed up in accordance with GP-centre routines.

6.5: Procedures for Blood sampling and analysis.

Blood will be drawn via a cubital vein and separated into serum by centrifugation. Two ml serum will be sent Vitas for Osteocalcin analysis and 2 ml send for K2 analysis at the

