The participants will receive all the Jarlsberg cheese in the study for free. Additionally, they will get the clinical examination for free and receive a moderate economical compensation. In case they get extra transportation costs for the participation, this will be covered by the study.

IX. Data Management

9.1: Electronical Case Record Forms (eCRF)

The validated electronical data management system InCRF will be used for collecting the data. Mainly the data will be entered on eCRFs by the responsible investigator at stage. Prior to study start; a data entry instruction document will be made. In this study a copy of source data will be collected on a paper. Source data consist of both printouts from the laboratory. In case of printing CRF data from InCRF instead of using paper CRF, it is important that also these are stored. The printed CRF data need investigator's signature and date.

9.2: Study Database

The validated data management system InCRF will be used for collecting the CRF data. The system selected is compliant with GCP guidelines and subject to 21 CFR (Code of federal regulations) FDA part 11 requirements. The final database will be stored in the Statistical Analysis system (SAS ver. 9.4 or later).

9.3: Data handling

The DM will perform the data checks. Once all the errors or issues are corrected or resolved, the investigator shall sign all the eCRFs to acknowledge all the data in the database has reviewed and corrected. After all the eCRFs has electronically signed by the investigator, the Study Statistician will perform final SAS checks and proof reading of safety listing. Thereafter, the database can perform final database hard lock.

The database will be transformed to a labelled SAS database, which also will be locked to prevent all possible changes or additions. In this copy, the responsible statistician can make derivations but no corrections of the data. If corrections are needed, the main basic study database must be re-opened and corrected. The international procedure for such changes will be followed.

X: Discontinuation of treatment

A XCS may discontinue from the study at any time if in the view of the Investigator it is in the participant best interests. Alternatively, the XCS has the right to discontinue the consent and exit the study without prejudice regarding his/her future treatment or care. If a XCS doesn't show up to an agreed visit the investigator should try to motivate the XCS to continue.

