10.1: Discontinuation not related to the study question

XCS discontinues the study of administrative reasons or reasons documented not related to the trial treatment will be classified as "Drop out" and replaced by new XCS. The dropouts will be described specially in the statistical analysis.

10.2: Discontinuation related to the study question

XCS discontinues the study of reasons related or might be related to the trial treatment will be classified as "Withdrawal". These will not be replaced by new XCS but included in both the Per-Protocol (PP) and the ITT analysis using the procedure "Last observations carried forward" (LOCF).

XI Statistical Model

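### The protocol does not separate stopping the cheese from leaving the study, so obtainable week-24 outcomes may be replaced by baseline carried forward

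*Protocol*

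**What the plan says.** Two places in the Protocol stop the cheese.

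- **Section 6.2.3, Comparative phase 2.** The trigger is "In case of AE of grade 3 or 4 according to CTCAE occur for more than three days, the responsible investigator will act". The consequence is "The intake of cheese will be stopped and the XCS will be followed up until the symptoms disappear". What is recorded is the interval to resolution ("The total duration from the last intake of the cheese to the disappearance of the symptoms will be recorded in days") and the treatment procedure.
- **Section 6.4, Stopping rule.** For a life-threatening or serious adverse event, "the cheese intake must stop, and the participant treated and followed up in accordance with GP-centre routines".

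The section that should give such a skier's status is headed "X: Discontinuation of treatment", but it opens with "A XCS may discontinue from the study at any time if in the view of the Investigator it is in the participant best interests" and then defines two classes, both for people who leave:

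- **10.1:** leaving for administrative or documented unrelated reasons makes the skier a Drop out, who is replaced.
- **10.2:** the other class reads "XCS discontinues the study of reasons related or might be related to the trial treatment will be classified as" Withdrawal. Of these it says "These will not be replaced by new XCS but included in both the Per-Protocol (PP) and the ITT analysis using the procedure" of last observation carried forward (LOCF).

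Comparative phase 2 of section 6.2.3 also begins by having all participants of both groups attend at weeks 16 and 24. It neither includes nor excepts skiers who have stopped the cheese.

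**The concern.** A skier can be off cheese and still be in the trial, but section X has no status for that. An investigator who has stopped the cheese finds a description of adverse-event follow-up and then two classes that both assume departure. Following section X, the skier becomes a Withdrawal or a Drop out, and later values are imputed or the skier is replaced.

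This matters most for the variables with a single post-baseline measurement. The flow chart in 1.10 places DXA (BMD, TBS), RMR, LM, muscle strength and peak VO2 at weeks 0 and 24 only. Section 5.1 calls BMD the most central variable of the second part. For these, the last observation before week 24 is the baseline, so LOCF records no change at all. For osteocalcin and the bone markers, LOCF carries forward an interim value instead.

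Neither stopping rule requires the event to be related to the cheese, and the definition of a serious event in 5.12.3 includes any hospitalisation. A skier whose event has resolved may be well enough and willing to attend. The trial is open, so the decision to stop could differ between arms. Later analysis cannot recover a measurement that was not taken, so this belongs in the protocol.

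**Working it through.** **1. The sections side by side**

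| Question | 6.2.3 phase 2, opening | 6.2.3 phase 2, AE rule | 6.4 | Section X, 10.1, 10.2 |
|---|---|---|---|---|
| Covers skiers off cheese? | Not addressed | Yes | Yes | Only if they leave the study |
| Outcome visits continue? | Yes, for all participants | Not stated | Not stated | Implicitly no: LOCF or replacement |
| What is recorded? | Scheduled measurements | Days to resolution, treatment | GP-centre follow-up | Last value carried forward (10.2) |

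The first column keeps everyone in the schedule. The last provides for missing later values. Nothing says which applies to a skier who stops cheese but does not leave.

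**2. The plan's own sample size**

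Inputs (section 11.3): 5% level (two-sided assumed, since sidedness is not stated), 90% power, difference of 1 SD.

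- Normal approximation: n = 2 × (1.960 + 1.282)² ≈ 21.01, so 22 per group.
- Noncentral t: 23 per group (power 0.8997 at 22, 0.9125 at 23).
- The stated 24 is close to this and slightly conservative (t-test power 0.924).
- 24 / (1 − 0.20) = 30, so the step to 30 matches an implied 20% dropout, which the protocol ties to the first part of the study.

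The figure reproduces. This point does not change it.

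**3. Scale of carrying baseline forward**

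Each stopper handled as a withdrawal is 1/30 = 3.3% of an arm.

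For illustration, suppose k of 30 Jarlsberg skiers are given zero change. Assume also a true difference of 1 SD, no mean change under Norvegia and an unchanged SD. The expected difference is then (1 − k/30) SD.

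| k | Difference (SD) | t-test power, 30 per group |
|---|---|---|
| 0 | 1.00 | 0.968 |
| 1 | 29/30 = 0.97 | 0.957 |
| 2 | 28/30 = 0.93 | 0.945 |
| 3 | 27/30 = 0.90 | 0.929 |
| 6 | 24/30 = 0.80 | 0.861 |

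Two limits apply. The 1 SD difference is the plan's assumption for total osteocalcin, and no effect size is given for BMD or the other week-24 variables. The table also takes a full response in the stoppers as its reference. Their observed values off cheese could show less than that, and only a measurement would tell.

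**The case against.** The strongest reply is that this is silence and not a rule. No section cancels a visit. Follow-up to symptom resolution is adverse-event follow-up and does not say that participation ends there. Comparative phase 2 of section 6.2.3 has all participants attending weeks 16 and 24, and sections 1.9 and 6.7 give 24 weeks for each participant. Section X tells the investigator to encourage a skier who misses a visit to continue. Section 5.12.2 codes the action taken on treatment (interruption, discontinuation) separately from leaving the study.

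Much of this stands, and it rules out three stronger readings that a reader might infer:

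- **That the outcomes of stoppers are uncollected by design.** The text does not say so, and the general visit schedule read literally says otherwise.
- **That safety observation ends when symptoms resolve.** The flow chart in 1.10 records adverse events at all five visits, and 5.12.2 asks for the outcome at the last visit.
- **That stoppers also lose their week-8 data.** The quoted rule sits in phase 2, which starts at week 8, so it does not govern events in phase 1. Section 6.4 has no phase limit but covers only life-threatening and serious events.

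It is also fair that few stops may be expected. Known milk-product allergy is an exclusion (3.2.2), section 8.1 reports no known adverse events apart from milk intolerance, and the trigger in 6.2.3 is a prolonged severe event. Nor would withdrawals vanish from the comparison, since 10.2 keeps them in both analyses.

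That last point leads back to the core. They are kept with carried-forward values, which for the week-24-only variables means baseline. The general schedule does not settle the matter either, because it does not mention skiers off cheese and section X gives them no status other than departure.

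**Conclusion.** The point holds as a failure to separate two events, stopping the cheese and leaving the study, across sections 6.2.3, 6.4 and X. It does not show that outcomes will be lost. It shows that a reasonable investigator following section X could end collection for a skier who would attend, and that the analysis would then record zero change for BMD, TBS, LM, RMR, strength and peak VO2.

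The size depends on the number of stoppers, which the protocol does not give. Each is 3.3% of an arm. Under the assumptions shown, one to three affected Jarlsberg skiers would shrink a 1 SD difference to between 0.97 and 0.90 SD. The direction is not guaranteed: stoppers in the Norvegia arm, or a change that both groups share over 24 weeks, would alter it.

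This should be corrected. It is more than a missing detail, because section 10.2 as written puts an assumed value where a real one could be had. No view is taken on when cheese should be stopped.

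**What to change.** Reconcile 6.2.3, 6.4 and section X (with 10.1 and 10.2) on data collection:

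1. State that a skier who stops the cheese stays in the study and is asked to attend all remaining scheduled outcome visits, with physical tests as fitness allows, unless consent to follow-up is withdrawn.
2. Record the date of last cheese intake.
3. Use the values observed after stopping in the ITT analysis.
4. Reserve the class Withdrawal in 10.2 for skiers who actually leave the study.
5. In 6.2.3, make clear that attendance at weeks 16 and 24 includes skiers off cheese.

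Leave the clinical stopping criteria in 6.2.3 and 6.4 as they are.

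The cost is a few sentences and a small effort to bring back a few skiers for visits already planned. The sample size does not change.

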6.3.1 Administration and doses

At baseline (week 0) the female and male strata will be provided a cheese sample for 4 weeks consumption of the type of cheese group they are allocated into. The female participants will be provided a sample resembling 75 grams cheese (5 slices) a day, and the male participants

will be provided 90 grams (6 slices) per day. The dose of Jarlsberg and Norvegia cheese is equal, and the dose is fixed due to OED from the former dose-finding study. After 4 weeks all participants will be provided new cheese samples of their study cheese. This will be repeated every 4 weeks till the end of the study at 24 as described previously. The dose of Jarlsberg and Norvegia cheese is equal.

Energy Sources	Jarlsberg Cheese	Norvegia Cheese
Total Energy	1458 kJ (351 kcal)	1458 kJ(351kcal)
fat	27g	27 g
carbohydrates	0 g	0 g
protein	27g	27g
calcium	770mg	820mg
phosphate	550mg	590mg

Tabell II: Cheese Energy Contents per 100 grams

6.3.2 Cheese supply, packing and storage.

The cheese will be delivered in 250-gram packages. The participants will receive the cheese by the investigator every 4 weeks. Both the Jarlsberg- and the Norvegia cheese used in the study will be given free of charge to the participating athletes.

Each package is labelled in accordance with the procedure for clinical trials. Additionally, the participants will be informed on how to perform the intake of the cheese and to store the cheese in a refrigerator at a temperature from 4° to10°C. Expiry date will be printed on the label.

Description	For use only in clinical trial
Trial substance	Type of cheese
Expire date	
Administration	Oral intake
Investigator	
Name of exporter	TINE A/S:
[contact]
Study	Comparative study in Active XCS
EudraCT number	2022-003264-24
Protocol id	XCS-Jarlsberg/IIA
Storage	Refrigerator between 4° to10°C

Table III: Label on each package

6.4: Stopping rule

In case of life-threatening AE or Serious Adverse Events (SAE) occurs, the cheese intake must stop, and the participant treated and followed up in accordance with GP-centre routines.

6.5: Procedures for Blood sampling and analysis.

Blood will be drawn via a cubital vein and separated into serum by centrifugation. Two ml serum will be sent Vitas for Osteocalcin analysis and 2 ml send for K2 analysis at the

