The first clinical investigation in the study will take place and is denoted as Day 0. The participants will receive a study identification number and be informed not to use other cheese than the one received in the study. During this initial clinical examination, all demographic data, social factors, history of disease and vital signs will be recorded. Blood samples will be drawn fastening for measurements of Osteocalcin and vitamin K2; Haematological and biochemical variables like HbA1C and Lipids, magnesium, calcium, phosphate, and urea; Collagen (CTX-1) and procollagen (PINP), parathyroid hormone (PTH), and bone specific alkaline phosphatase (BALP); Estradiol and testosterone; LH, FSH and SHBG. Additionally, a DXA with VAT and Bodyfat (BF) investigation will be performed. In addition to BMD and TBS, the body composition variables Lean body mass (LM) and Fat free mass (FFM), will be measured together with RMR, muscle strength and Peak VO2 before starting the clinical part. After four weeks the participants will meet for the second visit. Blood samples for

measurements Osteocalcin and the specific bone turnover markers (BTM) will be drawn. The participants will be given a new sample of cheese and calcium tablets for the next four weeks and new date for the next visit.

Diet registration for four days will be performed in the data application every 8 weeks in the study. The diet registration will be monitored by a professional nutritionist.

The last investigation in this first comparative part of will take place at week 8. The participants will undergo a common clinical examination like the one performed initially. Blood samples for measurements of Osteocalcin, vitamin K2, and BMT will be taken. Haematological and biochemical variables except for vitamin D, parathyroid hormone (PTH), Estradiol and testosterone; LH, FSH and SHBG will be measured.

1.6.3 Second comparative part:

The duration of the second comparative part is 16 weeks and starts at study-week 8. The participants will receive new cheese, and calcium tablets every 4 weeks and meet for new clinical examination every 8 weeks.

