The first clinical examination the this second comparative part will be performed at studyweek 16. A diet registration will be performed the last week before the visit. A common clinical examination will be performed and blood samples for measurements of Osteocalcin, vitamin K2, the specific BTMs, sex hormones and biochemical variables will be drawn. The participants will be given new sample of cheese and calcium tablets for four weeks and a date for the next visit.

This visit performed at week 24 is the last in clinical examination in the study and equal to the initial study visit. Blood samples will be taken for measurements of Osteocalcin, BTMs, vitamin K2 and biochemical and haematological variables. Sex hormones, muscle strength, Peak VO2, DXA investigation for BMD, TBS and LM, and RMR will be measured in the same way as at day 0.

The female participants will be interviewed about their menstruation status including menarche length, cycles day and use of hormonal contraception.

1.6.4 Dietary Monitoring:

The participants will fill in their dietary intake in an application at baseline and every 8th week of the study. During the last visit an Eating Disorder Examination Questionnaire- Short, (Prenjak K, et al BMC Psychiatry 2020;20:1–7) derived from EDE-Q © Fairburn and Beglin, 2008 will be a part of the interview.

The questions will be woven into the anamnestic interview and not as a questionnaire to ensure that the participants do not suffer from disordered eating.

1.7: Main variables

The main variables in this study will be the Osteocalcin development, BTMs, RMR and BMD. Supporting variables are muscle strength, LM and Peak VO2 and gender hormones. The vitamin K2 variants MK-7, 8, 9, 9(4H), HbA1C, vitamin D, Ca^{++,} Mg⁺⁺ and urea, will be secondary variables. As safety variables, haematological- and biochemical variables and adverse events (AE) will be recorded at each visit. The participants' activity will be continuously recorded.

1.8: Sample size

With a significant level of 5%, a power of 90% and a clinically relevant difference in total osteocalcin increase of one-time SD between the two groups, at least 24 XCSs in each group must be included. By correcting for dropouts during the first part of the study, 30 XCS will be included in each group. Totally 60 XCSs will be recruited for participation.

1.9: Study duration

The duration of the study will be 24 weeks for each participant.

Recruitment period of XCS	01.01-31.05.23

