Inclusion of the first participant	17th April 2023
Inclusion of the last participant	28 th April 2023
Last participant finalized comparative study part	23 rd June 2023
Last patient finalized follow-up part	14 th Oct 2023

1.10: Flow Chart

	Сог	nparison pa	rt I	Comparis	son part II
	Week 0	Week 4	Week 8	Week 16	Week 24
Jarlsberg cheese group	Х		Х	х	Х
Norvegia cheese group	Х		Х	Х	Х
Inclusion / Exclusion	Х				
criteria.					
Patient factors	X				
history of disease					
Concomitant treatment	Х	Х	Х	Х	X
Diet registration	Х		Х	Х	X
Vital signs	Х				X
- Blood pressure	Х				X
- Pulse rate	Х				Х
- Body weight	Х				X
Blood sampling					
Bone specific markers	Х	Х	Х	Х	X
Osteocalcin-Vitamin K	Х	Х	Х	Х	X
-HbA1C & Lipids	Х				X
-Vitamin D	Х				X
Sex Hormones	Х		Х	Х	Х
-Haematological	Х				Х
-Biochemical	Х		Х	Х	Х
DXA; BMD, TBS, RMR	Х				Х
LM, MS & Peak VO2	Х				Х
Physical training	Х		Х	Х	X
Menstruation status					Х
Adverse Events [CTCAE]	X	X	Х	Х	Х
Cheese compliance		Х	х	х	Х
End-of-study					Х

II: Introduction

2.1: Background

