5.7.3 Bone Turnover markers

Collagen 1 (CTX-1) Procollagen 1 (PINP) Parathyroid hormone (PTH) Bone specific alkaline phosphatase (BALP)

5.7.4 Sex hormones:

Estradiol Progesterone Testosterone LH FSH

5.7.5: Haematology

Haemoglobin (Hgb) HbA₁C

5.8: Diet registration

Diet registration will be performed by the participants. The daily intake of all food will be recorded daily for four days consecutively at screening and every eight weeks during the study. A pre-evaluated questionnaire based "diet.no" will be used and recorded on an electronical diet APP by the participants. The diet registration will be supervised by a qualified monitor. The results will be evaluated by the investigating team.

5.9: Menstruation status

To control the hormone blood sample results to female XCS, this group will be interviewed about their menstruation status. This includes menarche length, cycles day and use of hormonal contraceptives.

5.10: Cheese, supplement, and activity registration

The cheese, supplement of vitamin D and activity will med recorded in a form for daily registration. The activity will be recorded weekly. The parameters to be recorded are low- and high intensity running and roller-ski in hours, and low- and high-load strength exercise. The forms are handed out every fourth week of the study and collected by the investigator or the research assistant.

5.11: Compliance

The participants must eat their daily prescribed dose of cheese and vitamin D, register their activity weekly, and fill in their diet APP 4 days before their control every 8 weeks.

5.12: Adverse Events (AE)

5.12.1: Common Terminology Criteria for Adverse Events version 4.0 (CTCAE)

The CTCAE is divided in 26 System Organ Class (SOC) in accordance with the MedDRA hierarch. Within each SOC, AE are listed and accompanied by descriptions of severity or grade:

- Blood and lymphatic system disorders (11 Items)
- Cardiac disorders (36 Items)
- Congenital, familial, and genetic disorders (1 Items)
- Ear and labyrinth disorders (9 Items)
- Endocrine disorders (11 Items)
- Eye disorders (25 Items)
- Gastrointestinal disorders (117 Items)
- General disorders and administration site conditions (24 Items)
- Hepatobiliary disorder (16 Items)
- Immune system disorders (6 Items)
- Infections and infestations (76 Items)
- Injury, poisoning and procedural complications (78 Items)
- Investigations (38 Items)
- Metabolism and nutrition disorders (24 Items)

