Blood samples will be handled in accordance with the laboratory centre procedures, and the Common Terminology Criteria for Adverse Events (CTCAE) version 4.0 registered. The next step in the program is then lunch and rest for approximately 2 hours.

After lunch they will start with the VO2 tests on treadmill and be sent for the muscular strength tests. Both VO2 test and muscular strength tests will be supervised by qualified master students.

6.2.3 Comparative phase 1:

The XCS will randomly be allocated (1:1) to either daily intake of Jarlsberg cheese or Norvegia cheese. The daily intake of Jarlsberg cheese will be the OED for XCS and the comparative dose of Norvegia. The two cheese doses are nearly equal regarding total energy, protein carbohydrate and fat magnesium and calcium. The trial cheese can be consumed with other food at breakfast, lunch, or other meals during the day. The cheese may also be consumed heated/melted. All participants will be provided vitamin D supplement of $40\mu g/day$. The activity level is continuously recorded in the cheese-supplement – and activity record- form.

The participants meet for blood sampling in week 4 and 8 for measurements of Osteocalcin and Bone Turnover Markers (BTM). At week 8 week a clinical examination with measurement of vital signs and body weight will be performed. Additionally, blood samples will be taken for measurements of biochemical variables and vitamin K₂. The participants will be asked to fill in their diet for four days in the data application created for this study every 8 weeks. The diet registration will be performed and monitored.

6.2.3 Comparative phase 2:

All participants in both groups meet for the new investigation in week 16 and week 24, which is the last visit in the study. In both visits new clinical investigations will be performed with measurement of vital signs and body weight. During the last visit week 24, blood samples will be taken for measurements of Bone specific markers, vitamin K2 and biochemical variables. Sex hormones, muscle strength, Peak VO2 and DXA investigation of BMD,TBS, FFM and LM will be measured at in the same way as at day 0.

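### No adverse event recording is scheduled at the week-12 and week-20 cheese hand-outs, so in weeks 8 to 24 events that participants do not self-report depend on up to 8 weeks' recall

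*Protocol*

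**What the plan says.** **Contacts.** Protocol section 6.3.2 states "The participants will receive the cheese by the investigator every 4 weeks". Section 6.3.1 carries the supply through the whole study: "This will be repeated every 4 weeks till the end of the study at 24". Section 1.6.3 separates the two intervals in part 2: "The participants will receive new cheese, and calcium tablets every 4 weeks and meet for new clinical examination every 8 weeks". It also says that the cheese given at week 16 covers four weeks, while the next examination is at week 24, so a week-20 hand-out is needed. Section 5.10 adds an exchange of the daily cheese, vitamin D and activity forms: "The forms are handed out every fourth week of the study and collected by the investigator or the research assistant". No AE item is described for that form.

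**AE recording.** Section 1.7 lists AEs as a safety variable and says that "adverse events (AE) will be recorded at each visit". It does not say whether a hand-out counts as a visit. The row "Adverse Events [CTCAE" in flow chart 1.10 is marked at weeks 0, 4, 8, 16 and 24, and the AE row of diagram 6.8 shows the same time points. Neither has a week-12 or week-20 column. The text on comparative phase 2 (section 6.2.3) names only two visits: "All participants in both groups meet for the new investigation in week 16 and week 24, which is the last visit in the study".

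**Between visits.** Section 6.6 advises participants to contact the investigator about severe AEs and also about any other condition that bothers them.

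**The concern.** Part 1 has a scheduled AE enquiry every 4 weeks. Part 2 has one every 8 weeks, although the 4-weekly contacts continue. An AE that the participant does not volunteer between visits must then be remembered for up to 8 weeks.

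What is at stake is the quality of the AE record. Section 5.12.3 wants every AE described in detail with its severity and relationship to treatment, and the grading in 5.12.2 starts at mild. Mild and moderate events are the ones most likely to be forgotten or misdated over a long interval. The information could be collected at contacts that are already planned.

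**Working it through.** The plan gives no figure for AE recall, so there is none to reproduce. The check is interval arithmetic on the plan's own schedule.

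**Inputs**
- AE recording: weeks 0, 4, 8, 16, 24 (1.10 and 6.8).
- Cheese hand-outs: weeks 0, 4, 8, 12, 16, 20 (6.3.1 and 6.3.2; supply for the last four weeks is given at week 20).
- Follow-up: 24 weeks (1.9 and 6.7).
- Participants: 60 (1.8 and 11.3).

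**Hand-outs without scheduled AE recording:** weeks 12 and 20.

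**Length of each AE interval**

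| Interval | Current plan | With weeks 12 and 20 added |
|---|---|---|
| 0 to 4 | 4 weeks | 4 weeks |
| 4 to 8 | 4 weeks | 4 weeks |
| 8 to 16 | 8 weeks | 4 + 4 weeks |
| 16 to 24 | 8 weeks | 4 + 4 weeks |

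**Longest recall:** 8 weeks (56 days) now, 4 weeks (28 days) after the change.

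**Time inside an 8-week interval:** 8 + 8 = 16 of 24 weeks (67%). This overstates the exposure, because an event in the second half of such an interval is no further from the next enquiry than any event in part 1.

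**Time more than 4 weeks before the next enquiry:** the sum of max(0, gap − 4) is 0 + 0 + 4 + 4 = 8 of 24 weeks (33%). This is the fairer measure. It falls to 0 after the change.

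**Mean recall**, assuming that events are spread evenly over time and reported only when asked, is the sum of gap²/2 divided by 24:
- current plan: (8 + 8 + 32 + 32)/24 = 80/24 = 3.3 weeks;
- with weeks 12 and 20: (6 × 8)/24 = 48/24 = 2.0 weeks.

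**Added work:** 60 × 2 = 120 short enquiries at most.

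**The wording of 1.7.** If a hand-out is a visit, both schedules omit two AE time points. If it is not, the 8-week gaps are real. Either way the text and the schedules need an edit to agree on what happens at weeks 12 and 20.

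**The case against.** The strongest defence is that this is a legitimate design choice. The AE rows of 1.10 and 6.8 agree with each other and with the 8-weekly examinations of part 2. Section 8.1 describes a commercially available cheese with no AEs known to the authors except in people intolerant of milk, and known milk product allergy is an exclusion. A denser first 8 weeks, then sparser enquiry with an open self-report route, is defensible. That stands, and it is why the point is minor. It does not explain why two contacts that already take place go unused.

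Four stronger conclusions might be inferred, and the protocol does not support them.

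- **That all AEs in part 2 rest on 8 weeks' recall.** Section 6.6 covers any troublesome condition as well as severe events. Recall matters only for events the participant does not report.
- **That serious events would be missed.** Section 6.2.3 says "In case of AE of grade 3 or 4 according to CTCAE occur for more than three days, the responsible investigator will act". An enquiry every 28 days serves a three-day criterion no better than one every 56 days, and part 1 has the same dependence. On that timescale only contact by the participant helps, and 6.6 provides for it.
- **That part 2 AE counts would look falsely low against part 1.** No such comparison is planned. Section 11.2 plans comparisons between the groups.
- **That the gap biases the comparison of the cheeses.** Both arms have the same schedule. The trial is open, so self-reporting could differ by arm, but answers to a prompted question are unblinded too, and the protocol gives no figure for the size of any such difference.

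A practical objection also stands in part: 5.10 allows a research assistant to collect the forms, and that person may not be the one to grade an event or judge causality.

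**Conclusion.** The point holds in a limited form. AE recording is scheduled at weeks 0, 4, 8, 16 and 24 and omits the hand-out contacts at weeks 12 and 20. In weeks 8 to 24 the longest recall for events not self-reported is 8 weeks, against 4 in part 1. Under the even-timing assumption above, mean recall for such events over the study is 3.3 weeks and would be 2.0 with the two added enquiries.

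The consequence is mainly less complete and less well-dated recording of mild or moderate events. The number of events lost cannot be estimated from the protocol. The conclusion assumes that the hand-outs at weeks 12 and 20 are in-person contacts, as 6.3.2 indicates, and that staff would follow the schedules, which show no AE recording then. It is a cheap improvement to the safety data and has no bearing on the planned efficacy comparisons.

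**What to change.** - Add week-12 and week-20 columns, labelled as cheese hand-out contacts, to flow chart 1.10 and diagram 6.8.
- Mark AE recording in those columns in both, and cheese compliance in 1.10. Compliance is now marked only at weeks 4, 8, 16 and 24, although the forms are exchanged every fourth week.
- Reword 1.7 so that AEs are recorded at every visit and also at every 4-weekly hand-out.
- State that when a research assistant takes the report, the investigator grades the event and assesses its relationship to treatment.

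The cost is a schedule edit, a short eCRF page, a few minutes per participant at two existing contacts, and the investigator's time to grade whatever is reported. No new visit or procedure is needed, and the rules on dose and stopping are untouched.
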